7.4. Responsibilities for Reporting Adverse Events

The Investigator will record all adverse events per Section 7.1 definition that occur during the study period in the appropriate source documents and/or AE case report form with 10 calendar days of the date reported to the enrolling site. The study period for reporting adverse events (e.g., from the time of randomization to final study visit) will be 6 months, the local IRB will be notified by the enrolling site per local IRB regulations. The Investigator will comply with local regulations regarding the reporting of adverse events. Adverse events reported by enrolling sites will be promptly reported to Data Coordinating Center Institutional Review Board, NIH, and FDA per local regulations. Similar to other clinical trials conducted by University of Rochester investigators, adverse events will be immediately reported to the Coordination and Data Center (CDC) via dedicated web-based case report forms to the PI ([name]) and Co-PI ([name]). The CDC will be forwarding relevant documents to the Chair of DSMB for review and Chair will determine whether individual case will require immediate assessment by full DSMB committee or it could be assessed during electively scheduled DSMB meeting. The main point of assessment by DSMB will be to judge whether given adverse event could be related to AV junctional ablation.

8. RISK/BENEFIT ASSESSMENT

8.1. Potential Risks

Early risk to patients: The ablation catheter needs to be introduced through the femoral veins. This can result in either bleeding (hematoma) or thrombosis. The former was reported in 1 of 252 subjects (0.4%) in one study; the latter was reported in 1 of 156 subjects (0.6%) in another study. When the ablation is performed after implantation of the CRT device, it is possible to dislodge one of the implanted leads with the ablation catheter;

this was observed in 2 of 156 subjects (1.2%) in a prior study. This complication would require repositioning of the lead(s) that dislodged.

Late complications: There are 2 feared late complications of AV junction ablation. The first is that dislodgement of the ventricular lead in a pacemaker dependent subject could be fatal. However, a stable underlying escape rhythm is present in 67% of subjects following ablation. In addition, each subject in this trial will be undergoing biventricular pacing. It would be distinctly unusual for both the right and left ventricular leads to dislodge at the same time. Dislodgement of one ventricular lead would lead to loss of biventricular pacing but would still allow the other ventricular lead to pace the heart. In addition, contemporary left ventricular leads are multipolar, providing additional pacing redundancy.

The second feared complication is polymorphic ventricular tachycardia. In early trials of AV junction ablation, sudden cardiac death was observed in ~5% of patients. It was subsequently recognized that this was due to bradycardia-dependent polymorphic tachycardia. This adverse event can be eliminated by gradually reducing the lower pacing rate after initial programming is set at a higher than usual lower rate cutoff (as has been designed in this trial). Arrhythmic mortality was observed in only 2 of 252 subjects (0.8%) when such a protocol was routinely employed in a post-AV junction trial of pacemaker patients. In our study, all subjects will have an implantable defibrillator; thus, in the extremely rare event that a subject develops post-ablation polymorphic ventricular tachycardia, the defibrillator would be able to resuscitate the subject.

8.2. Protection Against Risks

All subjects that are treated for AF and heart failure with CRT are observed and treated in an optimal fashion as dictated by clinical standards to minimize any adverse events and to maximize the likelihood for clinical success. If the subject experiences any adverse event during the study, they will be treated in a manner consistent with clinical standards and the subject will be responsible for the costs of treatment.

8.3. Potential Benefits to Subjects

There is no guarantee of benefit from the AVJ ablation procedure. The study can provide better understanding of how to manage AF in the setting of HF in patients who will receive CRT. It is expected that the patient's heart failure status including symptoms and function, quality of life, and need for hospitalization could possibly improve.

8.4. Alternatives to Participation

Alternatives to participation are not to participate in the study and receive the same care outside of the formal study.

9. DATA AND SAFETY MONITORING PLAN

A data and safety monitoring board (DSMB) will be convened to independently monitor the conduct and the outcomes of the trial. The DSMB will be responsible for monitoring the safety and well-being of the subjects participating in this study and ensuring the ethical conduct of the trial. Since this study is a pilot project enrolling only 40 subjects and since the primary endpoint consists of echo-derived measures of LV function, the main focus of DSMB activity will be to monitor clinical adverse events that could be attributed to the procedure of ablation. Data on clinical events including procedural complications, HF events, ventricular tachyarrhythmias requiring ICD therapy, and death will also be collected by the study and provided to DSMB for evaluation of risks associated with AVJ ablation treatment in CRT patients. In the above capacities, the DSMB will be advisory to the Steering Committee responsible for overseeing the design, conduct, and data collection/analysis of the trial. The board will be comprised of 4 independent members: (1) a statistician with experience in clinical trials; (2) 2 cardiologists with expertise in HF clinical trials; and (3) 1 electrophysiologist with expertise in device implantation and experience with AVJ ablation. All cardiologists and the statistician selected for the DSMB must come from institutions not participating in the trial and have no personal or professional relationship with any participating investigator. The DSMB will meet before trial commencement and 4 times after each group of 20

subjects is enrolled. It is anticipated that these meetings will take place via conference call. One of the clinical cardiologists will be selected to chair the committee and will serve as the principal representative of the group.

10. CONFIDENTIALITY OF DATA AND INFORMATION STORAGE

Efforts will be made to maintain confidentiality of study data. All study data will be coded with an unidentifiable study code. The study coordinator for each enrolling site will locally maintain a key linking the subject's name with study data which will not be shared outside of the enrolling site. Subjects' personal information will be kept confidential and will not be released without his/her written permission, except as described in this section or as required by local law. Subject's personal information may be shared, to the extent necessary, among the research staff, with the Institutional Review Board and for research oversight as dictated by local regulations.

All information and data collected concerning subjects or their participation in this investigation will be considered confidential by the CDC. No social security numbers or direct identifiers will be collected by the CDC. Study data collected during this investigation may be used by the CDC for the purposes of this investigation, publication, to support future research and/or other business purposes. HIPAA authorization will be obtained from each subject by every enrolling site per local regulations and enrolling sites are expected to follow all local regulations related to data collection.

All data will be submitted using a password protected electronic data capture system with access limited to only those authorized by the Principal Investigator at each enrolling site per an electronic access request document with delegation made by the Principal Investigator. All study data will be coded with a study subject number that is assigned at the time of treatment randomization and cannot be linked to the patient's identify except at the individual enrolling sites. Source document records to support event adjudication or core laboratory analysis will be redacted of all PHI before being sent to the coordinating center and only the subject ID will be recorded to link the subject to this data. The electronic data will be directly extracted from web system for data collection.

11. STATISTICAL METHODS AND POWER CONSIDERATIONS

Overall Study Design and Primary Endpoint: This study is designed as a 2-arm unblinded randomized clinical trial. A total of 40 subjects receiving CRT-D will be randomized 1:1 to AVJ ablation or control arm (without AVJ ablation), stratified by enrolling site. The primary endpoint is the binary response defined as $\geq 15\%$ reduction in LVESV from baseline to 6 months.

Randomization Scheme: Enrolled subjects will be 1:1 randomized to AVJ ablation (with CRT-D) or control (CRT-D only). The randomization sequence will consist of a string of random 4- and 6-blocks. That is, there will be a 50% chance that the first block will consist of 4 subjects (2 AVJ ablation + 2 control, in random order), and a 50% chance that it will contain 6 subjects (3 AVJ ablation + 3 control, in random order). Each subsequent block will similarly be of random size. This procedure makes it very difficult for anyone to predict whether the next treatment assignment will be AVJ ablation (or control), helping to ensure integrity of the study. In contrast, if each block were of size 4, then it would be trivial to perfectly predict every 4th treatment assignment as well as the 3rd, if the first two were both AVJ ablation or both control, which would be undesirable. Randomization will be stratified by enrolling site. The randomization scheme will be generated by chief statistician [name] and provided to the CDC per Section 5.

Endpoint: The primary endpoint is the binary response defined as $\geq 15\%$ reduction in LVESV from baseline to 6 months.

Power and Sample Size: Randomizing 20 subjects per arm (for a total of 40 subjects), and allowing for up to 10% drop-out due to withdrawal, death, or inadequate imaging, we expect at least $n=18$ evaluable subjects per arm. This sample size will provide 80% power to detect an absolute change of 50% in response rates, using a 0.05 level 2-sided Fisher exact test, assuming the actual response rate in the AVJ ablation arm is 80-85%, as in

Gasparini 2006 (1) and Ferreira 2008 (6), where the empirical change in response rates was $\Delta = 49\%$ and 33% , respectively.

Crossovers: We anticipate that virtually no subjects will cross over from the AVJ ablation arm to the control arm. We expect at most 2-5% crossovers from control to the AVJ ablation arm, but we will work with investigators to consider these crossovers ideally only after trial completion so that they would have no effect on the primary endpoint. In any case, since the primary analyses will be conducted on an intention to treat (ITT) basis, crossovers will not affect the primary analysis. Furthermore, the stated response rates pertain to the planned ITT analyses, so they and the associated power computations already implicitly account for the small expected effect of the limited crossovers we anticipate for this study.

Statistical Methods: The primary analysis will be an intention-to-treat (ITT) analysis based on Fisher's exact test of the null hypothesis that the response rates are identical for both arms, conditional on the total number of responders. Response rates for each arm will be estimated by the empirical proportions (maximum likelihood estimates), along with associated Clopper-Pearson exact 95% confidence intervals (CI). Maximum likelihood estimates and associated 95% CI for the odds ratio (OR), relative risk (RR), and the absolute change in proportions will be used to summarize the treatment effect.

Secondary Analyses: Secondary endpoints include: a) change in LVEF from baseline to 6 months; b) LV end diastolic volume and change from baseline to 6 months; c) HF event including repeated HF events; d) all-cause mortality; e) VT/VF arrhythmic events requiring ICD therapy; f) inappropriate ICD therapy; g) percentage BiV pacing; h) quality of life; and i) complications related to AVJ ablation procedure. Since power for analyzing most secondary endpoints will be limited, secondary analyses will be mainly descriptive in nature. However, to the extent feasible, statistical analysis will be performed, as described briefly below.

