3. CHARACTERISTICS OF THE RESEARCH POPULATION

3.1. Subject Characteristics

a) Number of Subjects

This trial will enroll 40 subjects at 20-40 enrolling sites who meet study inclusion and exclusion criteria as described in Section 3.2.

b) Gender and Age of Subjects: Male of female subjects aged 21 years or older. We expect to enroll 25% women.

c) Racial and Ethnic Origin: There are no restrictions on race or ethnicity in this study. We expect to enroll 25% minority subjects.

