Randomization as a method of experimental control has been extensively used in human clinical trials. It prevents the selection bias and insures against accidental bias. It produces the comparable groups and eliminates the source of imbalance after treatment assignment. Finally, it permits the use of probability theory to express the likelihood of chance as a source for the difference of the final outcome. Randomization in this study will occur at visit 2. It should be noted that that visit 2 could take place on the same day as visit 1 and visit 3.

1. CRT-D device implantation or
2. CRT-D device implantation and AVJ ablation procedure

For subjects with an existing CRT-D device

1. Ablation
2. Medical management

Subjects will be notified that randomization is part of this study during the consent process. Subject will be informed which randomized arm they have received after completing the quality of life questionnaire. Subject will be notified that either treatment arm may be less or more effective, or may have more or less side effects.

Randomization will be stratified by enrolling site and generated per the scheme described in Section 11. The randomization strings for treatment assignment will be provided to the database programmer at the coordination site by chief statistician [name] and uploaded in the electronic data capture system with appropriate testing and validation that the system is working correctly prior to the beginning of subject

randomization. The enrolling site has full responsibility for completion of the CRFs required for subject randomization. The enrolling site may contact the data center project manager and will notify about randomization results only if the enrolling site has no internet access or the web base program will automatically assign the randomization treatment assignment and subject ID based on the randomization strings provided by the biostatistician. The randomization result is viewed by the enrolling site in the eDC system following randomization or documented on the paper CRF which is returned to the enrolling site if randomization cannot be done through the eDC system. All eligibility criteria will be confirmed prior to providing the randomization treatment assignment/subject ID to the enrolling site.

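### Random blocks of 4 and 6 within each site leave assignments easier to guess than Section 11 states, mainly at sites that reach a third subject (minor)

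*Combined protocol and SAP*

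**What the plan says.** Section 11 (Randomization Scheme) sets 1:1 allocation and states: "The randomization sequence will consist of a string of random 4- and 6-blocks". It gives the probabilities ("there will be a 50% chance that the first block will consist of 4 subjects", otherwise 6, and likewise for later blocks) and adds: "Randomization will be stratified by enrolling site". It then claims: "This procedure makes it very difficult for anyone to predict whether the next treatment assignment will be AVJ ablation (or control"). It contrasts this with fixed blocks of 4, which it considers undesirable because every fourth assignment, and the third after two alike, would be known.

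Three other statements bear on the claim:

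- Masking, Section 11: "This study is designed as a 2-arm unblinded randomized clinical trial".
- What sites learn, Section 5.1: "The randomization result is viewed by the enrolling site in the eDC system following randomization".
- Size, Section 3.1: "This trial will enroll 40 subjects at 20-40 enrolling sites".

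Section 5.1 also says that the assignment strings are loaded into the electronic data capture (eDC) system and that eligibility is confirmed before an assignment is released.

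**The concern.** With a separate list per site and open treatment, a site knows its whole sequence from the first subject, who also opens its first block. Each block must balance, so the arm that is behind is the likelier next assignment. Staff who can guess the next arm may, knowingly or not, choose whom to approach, or when, in line with the guess. The resulting selection bias is not removed by the intention-to-treat analysis, which keeps the groups as assigned. Nor is it removed by the blinded echo core lab, which protects measurement only. The stated property is also the plan's reason for preferring this scheme to fixed blocks, so it should be accurate.

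**Working it through.** **Inputs.** From Section 11: 1:1 allocation, block size 4 or 6 with probability 1/2 each, one list per site. From Section 3.1: 40 subjects, 20 to 40 sites. The documents do not say how subjects will be distributed over sites, so that is assumed below and a range is shown.

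**The plan's own comparison.** In a fixed block of 4, three assignments always leave one arm short by one, so the fourth is certain (100%). The first two are alike with probability 1/3, and then the third is certain. Both statements in Section 11 reproduce.

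**The planned scheme, by position within a site.** The rule is to guess the arm that is behind, and to toss a coin if the arms are tied.

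- Second: 0.5 × 2/3 + 0.5 × 3/5 = 0.633.
- Third, after two alike: the probability that the block is a 4 is (1/3) / (1/3 + 2/5) = 0.4545. The chance of a correct guess is 0.4545 × 1 + 0.5455 × 3/4 = 0.864.
- Third, overall: a block of 4 gives 1/3 × 1 + 2/3 × 1/2 = 0.667; a block of 6 gives 2/5 × 3/4 + 3/5 × 1/2 = 0.600; the mean is 0.633.
- Fourth: a block of 4 gives 1; a block of 6 gives 0.1 × 1 + 0.9 × 2/3 = 0.70; the mean is 0.85.
- Certainty at the fourth needs three alike, which only a block of 6 allows: 0.5 × 2/20 = 0.05.

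| Position at site | Correct guess, 4/6 blocks | Next assignment certain, 4/6 blocks | Correct guess, fixed 4 |
|---|---|---|---|
| 1 | 50.0% | 0% | 50.0% |
| 2 | 63.3% | 0% | 66.7% |
| 3 | 63.3% | 0% | 66.7% |
| 4 | 85.0% | 5% | 100% |
| 5 | 60.0% | 20% | 50.0% |
| 6 | 81.7% | 20% | 66.7% |

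A guesser who also uses the printed block sizes has the same hit rate at every position checked (1 to 12). Knowing the sizes therefore adds the occasional certainty but does not raise the average.

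**Over all 40 subjects.** If subjects fall at random on S equally likely sites, the expected number who are k-th at their site is S × P(Binomial(40, 1/S) ≥ k). For S = 20 this gives 17.43, 12.02, 6.47, 2.76, 0.96 and 0.28 for k = 1 to 6, and about 0.08 beyond. Weighting by the hit rates: (17.43 × 0.500 + 12.02 × 0.633 + 6.47 × 0.633 + 2.76 × 0.850 + 0.96 × 0.600 + 0.28 × 0.817 + 0.08 × about 0.6) / 40 = 0.591.

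| Enrolment pattern | Correct over all 40 | Expected certain, of 40 |
|---|---|---|
| 40 sites, one each | 50% | 0 |
| 40 sites, random spread | 55.2% | 0.06 |
| 30 sites, random spread | 56.6% | 0.14 |
| 20 sites, random spread | 59.1% | 0.39 |
| 40 sites, uneven (assumed) | 58.1–61.3% | 0.5–1.1 |
| 20 sites, uneven (assumed) | 61.8–64.7% | 1.2–1.8 |

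The uneven rows draw site shares from a Dirichlet distribution with parameter 1.0 or 0.3.

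**Possible bias.** Suppose every site acts on every guess and shifts the subject's response chance by +d when it expects ablation and by −d when it expects control (assumed). With 20 per arm, the arm difference is biased by 2d × (correct − wrong) / 40. With overall hit rate h this equals 2d(2h − 1).

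- h = 0.552: 2d × 0.104 = 0.21d.
- h = 0.591: 2d × 0.182 = 0.36d.
- h = 0.647 (most uneven case): 2d × 0.294 = 0.59d.
- One subject per site: 0.

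**The case against.** The strongest defence is that the claim is relative and the enrolment thin. At 1 to 2 subjects per site on average, most subjects are first or second at their site. Mixed blocks cut certainty at the fourth position from 100% to 5%, a real gain over fixed blocks of 4. All of that stands, and it keeps the point minor. It does not rescue the wording: at the fourth position the best guess is still right 85% of the time.

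Three stronger readings are tempting, and the documents do not support them.

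- *Allocation is not concealed.* A reader might infer this from the predictability. Section 5.1 has the eDC release each assignment only after eligibility is confirmed, which does conceal it. The plan's statement concerns how hard prediction is, and only that is overstated.
- *The next arm is often guessable.* The 63% for a second subject does not apply to everyone. With 20 sites of 2, the 20 first subjects are coin tosses, so the overall rate is (20 × 0.500 + 20 × 0.633) / 40 = 56.7%.
- *The result will be biased by several points.* The bias figures need every site to act on every guess, and nothing in the documents supports any particular d. For a given d and enrolment pattern they are upper bounds.

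It is also fair to say that stratifying by site is a legitimate preference. No calculation or analysis in the plan is wrong on this account.

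**Conclusion.** The concern holds as a minor one. The sentence in Section 11 is too strong for an open trial with a blocked list per site, and it fails most clearly where a site reaches a third subject after two alike (86%) or a fourth (85%). Across the trial the guesser's advantage over a coin toss is about 5 to 9 percentage points under random spread over 40 to 20 sites. It reaches about 15 points under very uneven enrolment and is nil at one subject per site. The bias could not exceed about 0.2d to 0.36d under random spread. As an illustration only, an assumed d of 10 to 20 points gives roughly 2 to 7 points, against the 50-point difference for which the trial is powered. The size depends on how unevenly sites enrol and on how staff behave, and the documents give neither.

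**What to change.** 1. Assign from one central blocked list across all sites, through the existing eDC. A site's own assignments then no longer show its place in a block. In simulation, with 20 sites of 2 arriving in random order, the second subject is the opposite of the first about 51% of the time, against 63% now.
2. Move the block sizes and their probabilities from the site-facing protocol to a restricted randomization document. This removes the occasional certainties. It does not lower the average hit rate, so it does not replace step 1.
3. Delete the sentence on difficulty of prediction, or limit it to what the adopted scheme delivers. If site stratification is kept, say that later assignments at a site are partly predictable.

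The cost is a new set of strings, their validation in the eDC and an edit to Sections 5.1 and 11. Balance within site is given up, but at 1 to 2 subjects per site most sites would not complete a block of 4, so little is lost.

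### Site-stratified blocks of 4 and 6 control the arm split poorly with 40 subjects at 20-40 sites, so 20 per arm and 18 evaluable per arm are not assured

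*Combined protocol and SAP*

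**What the plan says.** Section 3.1 states that "This trial will enroll 40 subjects at 20-40 enrolling sites". Section 11 (Randomization Scheme) allocates 1:1, with this blocking rule: "The randomization sequence will consist of a string of random 4- and 6-blocks". Each block has a 50% chance of being either size. The same paragraph adds "Randomization will be stratified by enrolling site", and Section 5.1 repeats it: "Randomization will be stratified by enrolling site and generated per the scheme described in Section 11". The sample-size paragraph of Section 11 takes 20 randomized per arm as given, "allowing for up to 10% drop-out due to withdrawal, death, or inadequate imaging", and from this expects no fewer than 18 evaluable per arm. Those 18 carry the claim of 80% power for a 50-point difference with a two-sided Fisher exact test at 0.05.

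No section describes pooling of small sites, a minimum enrolment per site, minimization or any constraint on the overall split. The primary test in Section 11 does not use site. The secondary linear models name baseline values and demographic characteristics as adjustment variables, not site.

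**The concern.** A permuted block forces equal arms only once it is full. With a separate block sequence at each site and a mean of one or two subjects per site, most sequences stop inside their first block, and the small imbalances left at each site add up over 20-40 sites. The sample-size paragraph nevertheless reads as if the scheme will produce 20 per arm.

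At stake is whether the per-arm numbers in the plan describe what the randomization will deliver. An arm with 17 or fewer randomized cannot supply 18 evaluable subjects even with no dropout.

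**Working it through.** **Inputs.** 40 subjects and 20-40 sites (Section 3.1). 1:1 allocation, blocks of 4 or 6 with probability 0.5 each, site strata, 20 per arm, 10% dropout, 18 evaluable per arm, and a response rate of 80-85% with ablation, hence 30-35% with control (Section 11).

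**Step 1: the plan's own figure.** Exact Fisher power with 18 per arm is 83.5% (80% v 30%) and 84.2% (85% v 35%). With 17 per arm it is 79.2% and 80.1%. So 18 is the smallest equal arm size that reaches 80% across the stated range, and 18 / (1 - 0.10) = 20 per arm. The plan's arithmetic reproduces.

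**Step 2: two cases in closed form.**
- One subject per site (40 sites): every subject is the first in a new block, so the size of the ablation arm is binomial(40, 0.5). SD = sqrt(40 × 0.25) = 3.16. P(20:20) = 12.5%. P(an arm has 17 or fewer) = 43%.
- Two subjects per site (20 sites): the chance that both get the same arm is 1/3 in a block of 4 and 2/5 in a block of 6, so 0.5 × 1/3 + 0.5 × 2/5 = 0.367. This is also the variance of the ablation count at one site. SD = sqrt(20 × 0.367) = 2.71.

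**Step 3: other spreads.** The documents do not say how subjects spread over sites, so this is an assumption. Each spread was simulated with 20,000 trials: even, random (equally likely sites), and strongly skewed (site rates drawn from a gamma distribution with shape 0.5). For a split n1:n2, the chance that both arms reach 18 evaluable is P(Bin(n1, 0.9) ≥ 18) × P(Bin(n2, 0.9) ≥ 18), averaged over the simulated splits.

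| Spread of the 40 subjects | SD of arm size | 20:20 | An arm with 17 or fewer randomized | Both arms with 18 or more evaluable, 10% dropout |
|---|---|---|---|---|
| One per site, 40 sites | 3.2 | 13% | 43% | 17% |
| Two per site, 20 sites | 2.7 | 15% | 35% | 20% |
| Random, 40 sites | 2.7 | 14% | 36% | 19% |
| Random, 20 sites | 2.3 | 18% | 28% | 22% |
| Strongly skewed, 40 sites | 2.2 | 18% | 25% | 23% |
| Strongly skewed, 20 sites | 1.8 | 22% | 16% | 27% |
| One central list, same blocks | 0.5 | 77% | 0% | 44% |
| Fixed 20:20 | 0 | 100% | 0% | 46% |

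The last row is P(Bin(20, 0.9) ≥ 18) squared: 0.677 × 0.677 = 0.458. The central list can never be worse than 19:21. Block sizes and 40 are all even, so a cut final block holds 2 or 4 subjects, and their arms differ by at most 2.

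**Step 4: effect on power.** With 36 evaluable subjects, Fisher power is about 86% or more at 16:20, 83-85% at 14:22, and first falls below 80% at about 12:24 (77-81%). Averaged over the simulated splits it is 84-86%. With the central list and a fixed 10% loss it is about 84-85%.

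**Step 5: effect on baseline balance.** The standard error of a chance difference in a baseline mean is proportional to sqrt(1/n1 + 1/n2). Relative to 20:20 it is 1.1% larger at 17:23 and 3.3% larger at 15:25.

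**The case against.** The best defence is that little inference is at risk. The allocation is still a concealed 1:1 randomization, and Fisher's test is valid at any split. Section 11 calls 18 an expectation, and random dropout alone would defeat it more often than not, even from a perfect 20:20 start. All of this stands.

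A reader might infer four stronger things that the documents do not support:
- *The scheme fails as a randomization, or is no better than tossing a coin.* It equals simple randomization only at one subject per site. With a random spread over 20 sites, about 31% of subjects are at sites with 4 or more, and the variance of the arm size is about half that of a coin toss (2.3² = 5.3 against 3.16² = 10).
- *The planned numbers cannot be reached.* Both arms have at least 18 randomized in 57% of trials at one subject per site, in 72% with a random spread over 20 sites, and in 84% with strong skew over 20 sites. The numbers are not assured, but they are not ruled out.
- *The 80% power is lost.* Step 4 shows that it is kept at all likely splits.
- *Baseline comparability is lost.* Step 5 shows that covariate balance hardly depends on the split. A central list leaves covariates almost equally to chance.

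It can also be said that the size of the effect rests on an assumed spread over sites. That is why a range is given. Even the most favourable spread in the table leaves an arm with 17 or fewer in 16% of trials, against none with a central list.

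**Conclusion.** The point holds as a mismatch between the randomization scheme and the per-arm numbers. With a mean of 1-2 subjects per site, site-stratified blocks of 4 and 6 are mostly unfilled and control the overall split poorly. The 16-43% chance that an arm falls short of 18 before dropout comes from the stratification alone. The failure to have 18 evaluable in both arms is shared: stratification cuts the chance of success from 44-46% to 17-27%, and random dropout accounts for the rest.

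These ranges rest on the assumed spreads, on independent 10% dropout, and on the absence of any balancing rule beyond those described. The power statement does not need to be withdrawn. It is a minor to moderate point, worth correcting because the remedy is cheap.

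**What to change.** - In Section 5.1 (the opening paragraph and the randomization text) and Section 11 (the design paragraph and Randomization Scheme), delete the stratification by enrolling site. Generate one central sequence of random 4- and 6-blocks for the whole trial, issued by the electronic data capture system.
- In the sample-size paragraph of Section 11, describe 18 evaluable per arm as the number expected at 10% dropout, not as a minimum.

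The cost is protocol wording and a new list, since the electronic system already issues assignments. Concealment does not suffer: a site sees only its own few assignments and not the order of the central list. The downside is that formal within-site balance is given up. The current scheme provides this only at the few sites that enrol 4 or more, and no planned analysis uses site.

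If the sponsor wants to keep a site element, pooling sites or minimization would also serve. Otherwise the plan should at least state the imbalance to be expected under the current scheme.
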